8.1.2. Temporary Discontinuation from Study Treatment

In certain situations after randomization, the investigator may need to temporarily interrupt study drug (for example, AE). If study drug interruption is due to an AE, the event is to be documented and followed according to the procedures in Section 9.2 of this protocol. Every effort should be made by the investigator to maintain patients on study drug and to restart study drug after any temporary interruption, as soon as it is safe to do so.

- If the number of consecutive missed doses is ≤ 2 , the treatment can be restarted at the same dose, if the drug was well tolerated prior to discontinuation,
- If the number of consecutive missed doses is ≥ 3 , then the treatment should be restarted at 5 mg or matched placebo irrespective of the dose the patient was receiving before the interruption and subsequently escalated as required by protocol.
- If the above situations occur again during the course of the study, the investigator in consultation with sponsor or designee will discuss the next treatment option.
- The investigator will use the IWRS to receive the appropriate study drug dispensing information to preserve blinding of the study drug

If the study drug interruption is due to intolerable persistent GI AE (for example, nausea, vomiting, or diarrhea), the patients should be treated as suggested in Section 7.8.2.5.

The data related to temporary interruption of study treatment will be documented in source documents and entered on the eCRF.

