7.1. Treatments Administered

Patients will be randomized in a 1:1:1:1 ratio to receive tirzepatide 5 mg, 10 mg, 15 mg, or placebo. Study drug will be administered QW as SC injection in patients with T2DM who are naïve to injectable therapy, inadequately controlled with diet and exercise alone, and have not been treated with any oral antidiabetic medication during the 3 months preceding to the start of the study.

Table GPGK.3 shows the randomized treatments for the entire treatment period.

The starting dose of tirzepatide will be 2.5 mg QW for 4 weeks, followed by an increase to 5 mg QW, for the duration of the study for the 5-mg group. For the 10-mg group, the starting dose of tirzepatide will be 2.5 mg QW for 4 weeks, then the dose will be increased by 2.5 mg every 4 weeks (2.5 mg to 5 mg to 7.5 mg to 10 mg) until the 10-mg dose is reached and maintained for the duration of the study. For the 15-mg arm, the starting dose of tirzepatide will be 2.5 mg QW for 4 weeks, then the dose will be increased by 2.5 mg every 4 weeks (2.5 mg to 5 mg to 7.5 mg to 10 mg to 12.5 mg to 15 mg) until the 15-mg dose is reached and maintained for the duration of the study.

Patients randomized to the placebo group will inject matched placebo subcutaneously QW for the entire treatment period.

It will not be possible for investigators and patients to know which treatment they are receiving.

Table GPGK.3. Treatment Regimens

Name of Drug	Dosage	Frequency	Drug Formulation	Route of Administration
Investigational Compound				
tirzepatide	5 mg	QW	Single-dose pen	SC
	10 mg	QW	Single-dose pen	SC
	15 mg	QW	Single-dose pen	SC
Comparators				
placebo		QW	Single-dose pen	SC

Abbreviations: QW = once weekly, SC = subcutaneous.

The investigator or his or her designee is responsible for the following:

- explaining the correct use of the investigational agent(s) to the patient. For SDP, a demonstration device will be used
- verifying that instructions are followed properly
- maintaining accurate records of investigational product dispensing and collection

Patients should return all study drugs to the site according to the Schedule of Activities (Section 2). Patients should be instructed to discard all used SDPs in a closeable, puncture-resistant container according to local regulations.

7.1.1. *Packaging and Labelling*

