8.1. Discontinuation from Study Treatment

8.1.1. Permanent Discontinuation from Study Treatment

Possible reasons leading to permanent discontinuation of investigational product:

- **Patient Decision**
 - The patient requests to discontinue investigational product.
- **Discontinuation due to increased risk of hypoglycemia**
Please refer to Section [7.8.2.2](#) for details.
- **Discontinuation due to a hepatic event or liver test abnormality**

Patients who are discontinued from investigational product due to a hepatic event or liver test abnormality should have additional hepatic safety data collected via an eCRF.

Discontinuation of the investigational product for abnormal liver tests **should be** considered by the investigator when a patient meets one of the following conditions after consultation with the Lilly-designated medical monitor:

- ALT or aspartate aminotransferase (AST) >8X ULN
- ALT or AST >5X ULN for more than 2 weeks
- ALT or AST >3X ULN and total bilirubin level (TBL) >2X ULN or international normalized ratio >1.5
- ALT or AST >3X ULN with the appearance of fatigue, nausea, vomiting, right upper quadrant pain or tenderness, fever, rash, and/or eosinophilia (>5%)
- alkaline phosphatase (ALP) >3X ULN
- ALP >2.5X ULN and TBL >2X ULN
- ALP >2.5X ULN with the appearance of fatigue, nausea, vomiting, right quadrant pain or tenderness, fever, rash, and/or eosinophilia (>5%)

In addition, patients will be discontinued from the investigational product in the following circumstances:

- If a patient is inadvertently enrolled and it is determined that continued treatment with study drug would not be medically appropriate, see Section [8.1.3](#)
- Acute or chronic pancreatitis
- If a patient is diagnosed with MTC after randomization or has a postrandomization calcitonin value ≥ 35 ng/L that has increased at least 50% over baseline
- If a patient is diagnosed with an active or untreated malignancy (other than basal or squamous cell skin cancer, in situ carcinomas of the cervix, or in situ prostate cancer) after randomization

- Any significant study drug-related hypersensitivity reaction
- Any other TEAE, SAE, or clinically significant laboratory value for which the investigator believes that permanent study drug discontinuation is the appropriate measure to be taken
- If female patient becomes pregnant
- If a patient is diagnosed with T1DM

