9.2.2.7. Hypersensitivity Events

All allergic or hypersensitivity reactions will be reported by the investigator as either AEs or, if any serious criterion is met, SAEs. Additional data, such as type of reaction and treatment received, will be collected on any AEs or SAEs that the investigator deems related to study drug(s) via a CRF created for this purpose. Additional samples should also be collected as outlined in Section 9.4.4. Study drug(s) should be temporarily interrupted in any individual suspected of having a severe or serious allergic reaction to the study drug(s). Study drug(s) may be restarted when/if it is safe to do so, in the opinion of the investigator. If study drug(s) is permanently discontinued, the patient will receive another glucose-lowering treatment, judged by the investigator to be appropriate based on the patient's clinical status, and will continue in the trial to collect all planned efficacy and safety measurements.

9.2.2.7.1. *Injection Site Reactions*

Injection site reactions will be collected on the eCRF separate from the hypersensitivity reaction eCRF. At the time of AE occurrence in the tirzepatide group, samples will be collected for measurement of tirzepatide anti-drug bodies (ADAs) and tirzepatide concentration.

9.2.2.7.2. *Anti-Drug Antibodies*

The occurrence of ADA formation will be assessed as outlined in Section 9.4.4.

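### Under Protocol 8.1.2, a patient held at 2.5 mg for a suspected severe or serious allergic reaction who misses three or more doses can be restarted only at 5 mg, with no sponsor consultation required first

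*Protocol*

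**What the plan says.** Four parts of the protocol act together.

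- **Dose schedule (7.1).** In each active arm, "The starting dose of tirzepatide will be 2.5 mg QW for 4 weeks". The next step is 5 mg in all three arms.
- **Hold for allergic reactions (9.2.2.7).** Study drug is interrupted when a severe or serious allergic reaction is suspected. Afterwards, "Study drug(s) may be restarted when/if it is safe to do so, in the opinion of the investigator". No restart dose is given.
- **Restart dose (8.1.2).** After up to two consecutive missed doses, the same dose may be resumed "if the drug was well tolerated prior to discontinuation". After three or more, "the treatment should be restarted at 5 mg or matched placebo irrespective of the dose the patient was receiving before the interruption", followed by escalation per protocol. For interruptions caused by adverse events, 8.1.2 points to Section 9.2 for documentation and follow-up only. Its one special case is gastrointestinal events. Sponsor consultation comes in only on recurrence: "If the above situations occur again during the course of the study, the investigator in consultation with sponsor or designee" will discuss what to do next.
- **Limits.** Section 8.1.1 requires permanent discontinuation for "Any significant study drug-related hypersensitivity reaction". Section 7.4.1 permits no dose adjustment. Section 9.2.1 requires serious events to be reported to the sponsor within 24 hours.

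**The concern.** The restart rule for long holds is protective for a patient on 7.5 mg or more, because it steps the dose down. Applied to a patient still in the 2.5-mg step, it steps the dose up. If the hold was for a suspected severe or serious allergic reaction, the first re-exposure is then larger than the dose that preceded the reaction.

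A blinded investigator who considers a cautious re-exposure acceptable has two choices, 5 mg or no restart, although 2.5 mg is the protocol's own starting dose. If the reaction was severe but not serious, nothing requires the sponsor to be consulted before the first restart. Allergic and hypersensitivity reactions are a listed safety objective, so the handling of these patients deserves an explicit rule.

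**Working it through.** **1. Restart dose relative to last dose.** Inputs: restart dose 5 mg (8.1.2); dose levels from 7.1. Ratio = 5 / last dose.

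| Last dose (mg) | 2.5 | 5 | 7.5 | 10 | 12.5 | 15 |
|---|---|---|---|---|---|---|
| Ratio | 2.0 | 1.0 | 0.67 | 0.5 | 0.4 | 0.33 |

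Only the 2.5-mg level gives a ratio above 1.

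**2. Calendar.** With no earlier missed doses, dose k (k = 1 to 4) is given at Week k − 1. After three missed doses the earliest restart is Week k + 3, that is Weeks 4 to 7, which is 28 days after the last injection. The scheduled dose in Weeks 4 to 7 is 5 mg in every active arm. The restart dose is therefore the calendar dose, but the patient has taken only k of the four planned 2.5-mg doses, and as few as one.

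**3. Affected window.** Four of 40 weekly doses (Weeks 0 to 39). The reaction must also be followed by three or more missed doses, no permanent stop under 8.1.1, and clearance by the investigator. Such a hold is plausible: 9.4.4 asks for a sample 30 days after onset of a hypersensitivity reaction, and an investigator who chose to wait for it would normally pass three weekly doses. The protocol does not require that wait. The documents give no event rate, and none is assumed.

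**4. How far this differs from the scheduled step to 5 mg.** Section 9.4.4 treats Visit 801 as 5 half-lives after end of treatment. Counting 28 days from the last treatment visit, or 35 days from the Week-39 dose, the half-life is 28/5 = 5.6 to 35/5 = 7.0 days. Assume one compartment, first-order loss and immediate absorption. Weekly carry-over is r = 2^(−7/5.6) = 0.42 to 2^(−7/7) = 0.50.

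- Scheduled step: amount after dose 5 divided by amount after dose 4 = 6.76/4.18 = 1.62 (r = 0.42) or 7.34/4.69 = 1.57 (r = 0.50).
- Restart after a 28-day gap: (5 + A·r⁴)/A, where A is the amount just after dose k.

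| Last dose taken | r = 0.42 | r = 0.50 |
|---|---|---|
| k = 1 | 5.08/2.5 = 2.03 | 5.16/2.5 = 2.06 |
| k = 2 | 1.44 | 1.40 |
| k = 3 | 1.28 | 1.21 |
| k = 4 | 1.23 | 1.13 |

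The rise in amount on board exceeds that of the scheduled step only after dose 1. After doses 2 to 4 it is smaller, although the injected dose still doubles.

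**The case against.** The strongest reply is that 8.1.1 already removes the patients who matter. A severe or serious allergic reaction attributed to the drug is hard to call anything but significant, and then the drug is stopped for good. For a reaction judged unrelated, the idea of a reaction dose has little meaning. This shrinks the group but does not empty it. Section 8.1.1 does not define significant, and 9.2.2.7 expressly provides for restart after a suspected severe or serious reaction, which includes cases of uncertain attribution.

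Four stronger readings are tempting, and the documents do not support them.

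- *The plan forces re-exposure at double dose.* It does not. Section 9.2.2.7 leaves restart to the investigator's view of safety, and the lead-in to 8.1.2 makes restart subject to safety for long and short holds alike. The missing tolerability condition in the long-hold bullet does not remove that.
- *Twice the dose means a greater allergic risk.* No passage says so. Sections 5.5 and 7.8.2.5 justify slow escalation by gastrointestinal tolerability. Section 3.2 implies that 5 mg was given without titration in earlier studies, though it also reports 5 mg as the maximum tolerated single dose in healthy subjects.
- *Gastrointestinal holds are handled more cautiously.* Section 7.8.2.5 omits one dose and resumes at the same dose, which agrees with the short-hold bullet of 8.1.2. There is no contrast.
- *The sponsor stays unaware.* Serious events are reported within 24 hours, and nothing bars voluntary consultation. The gap is that prior consultation is not required. For severe but non-serious reactions the 24-hour report does not apply either.

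The objection that 5 mg is already the calendar dose stands for timing. It does not answer the point that the patient may have received only one dose, and reacted to it.

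**Conclusion.** The point holds in limited form. At 2.5 mg, and only there, the long-hold rule raises the dose, by a factor of 2.0. A cleared patient in the group described has no lower restart dose available, and a first restart needs no sponsor consultation. The clearest case is a reaction after the first injection.

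This is a minor safety improvement. It rests on the text of 8.1.2, 9.2.2.7, 7.1 and 7.4.1, and on the cautious principle of not exceeding the reaction dose at re-exposure, not on evidence of dose-dependent allergic risk. The amount-on-board figures depend on the simple model stated above and are context only. Patients who reacted at 5 mg or above are not affected by the dose part. Few patients are expected, and nothing here bears on power, type 1 error or the efficacy conclusions.

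**What to change.** Add to the three-or-more-doses bullet of 8.1.2:

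> If the interruption was for a suspected severe or serious allergic reaction (Section 9.2.2.7) and Section 8.1.1 does not require permanent discontinuation, the restart dose is the lower of 5 mg and the last dose taken (2.5 mg or matched placebo if the last dose was one of the first four weekly doses), given for 4 weeks and then escalated as required by protocol. The investigator will consult the sponsor or designee before this restart. The dose is assigned through the IWRS.

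The wording is confined to severe or serious suspected reactions, so mild ones do not trigger consultation. It refers to the first four doses because the Week-4 dose is already 5 mg. All three active arms share the 2.5-mg step and placebo is matched, so the branch depends on the timing of the hold and does not reveal the arm.

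Cost: three sentences, one IWRS branch, and escalation 4 weeks later for patients restarted at 2.5 mg. At the shortest hold (restart in Weeks 4 to 7, steps every 4 weeks), the 15-mg arm now reaches 15 mg 16 weeks after restart, at Weeks 20 to 23. With the change it takes 20 weeks, so Weeks 24 to 27. That leaves 16 to 13 weeks at 15 mg before Week 40 instead of 20 to 17. The planned analysis is unchanged.

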8.1.3. Discontinuation of Inadvertently Enrolled Patients

If the sponsor or investigator identifies a patient who did not meet enrollment criteria and was inadvertently enrolled, then the patient should be discontinued from study treatment unless there are extenuating circumstances that make it medically necessary for the patient to continue on

study treatment. If the investigator and the sponsor CRP agree that it is medically appropriate to continue, the investigator must obtain documented approval from the sponsor CRP to allow the inadvertently enrolled patient to continue in the study with or without treatment with investigational product. Safety follow-up should be performed as outlined in Section 2 (Schedule of Activities), Section 9.2 (Adverse Events), and Section 9.4 (Safety) of the protocol.

8.2. Discontinuation from the Study

In order to minimize the amount of missing data and to enable assessment of study objectives as planned in the study protocol, every attempt will be made to keep patients in the study irrespective of the following:

- adherence to study drug,
- adherence to visit schedule,
- missing assessments,
- study drug discontinuation due to an AE,
- development of comorbidities, and
- development of clinical outcomes.

The circumstances listed above are not valid reasons for discontinuation from the study.

Patients will be discontinued in the following circumstances:

- Enrollment in any other clinical study involving an investigational product or enrollment in any other type of medical research judged not to be scientifically or medically compatible with this study
- Participation in the study needs to be stopped for medical, safety, regulatory, or other reasons consistent with applicable laws, regulations, and good clinical practice
- If a female patient becomes pregnant
- If a patient is diagnosed with T1DM
- Patient requests to be withdrawn from the study

Patients who agree to provide information relevant to any study endpoint at the end of the study are not considered to have discontinued from the study.

A patient who withdraws consent and clearly indicates that there will be no further contact of any kind with the site will be considered to have discontinued from the study.

Prior to early study discontinuation, the patient may discontinue study drug and will have end-of-study procedures (ET visit) performed as shown in the Schedule of Activities (Section 2). During the ET visit, the patient will not initiate any new glucose-lowering therapy. Visit 801 (safety follow-up visit) should be performed approximately 4 weeks after the ET visit as the final study visit.

Patients discontinuing from the study prematurely for any reason should complete adverse event and other safety follow-up per Section 2 (Schedule of Activities), Section 9.2 (Adverse Events), and Section 9.4 (Safety) of this protocol.

8.3. Lost to Follow-Up

A patient will be considered lost to follow-up if he or she repeatedly fails to return for scheduled visits and is unable to be contacted by the study site. Every attempt will be made to minimize the number of patients considered lost to follow-up at the end of the study. Patients will be informed about the importance of completing the study and providing updated contact information to the study site when necessary.

9. Study Assessments and Procedures

Section 2 lists the Schedule of Activities, with the study procedures and their timing (including tolerance limits for timing).

Appendix 2 lists the laboratory tests that will be performed for this study.

Unless otherwise stated in the subsections below, all samples collected for specified laboratory tests will be destroyed within 60 days of receipt of confirmed test results. Certain samples may be retained for a longer period, if necessary, to comply with applicable laws, regulations, or laboratory certification standards.

9.1. Efficacy Assessments

9.1.1. Primary Efficacy Assessments

The primary efficacy measurement in this study is mean change in HbA1c values from baseline to 40 weeks, as determined by the central laboratory. Blood samples for HbA1c measurements will be collected at specific clinic visits as summarized in the Study Schedule, Section 2.

9.1.2. Secondary Efficacy Assessments

The following secondary efficacy measures will be assessed at 40 weeks based on data collected at the times shown in the Study Schedule (see Section 2).

- Mean change in body weight
- Proportion of patients achieving a target HbA1c <7.0% (53 mmol/mol), ≤6.5% (48 mmol/mol), and <5.7% (39 mmol/mol)
- Mean change in FSG values measured in the central laboratory
- Mean change in daily average 7-point SMBG profiles
- Proportion of patients who achieved weight loss ≥5%, ≥10%, and ≥15%

9.1.3. Exploratory Assessments and Procedures

The following secondary efficacy measures will be calculated based on data collected at the times shown in the Study Schedule (see Section 2).

- Mean change in waist circumference
- Changes from baseline in mean BMI
- Mean change in lipids (total cholesterol, high-density lipoprotein, low-density lipoprotein, very low-density lipoprotein, and triglycerides)
- Biomarkers
- APPADL scores
- EQ-5D-5L scores
- IW-SP scores

9.1.4. *Body Weight, Height, Waist Circumference and Body Mass Index*

Body weight and waist circumference will be measured at prespecified time points (see Schedule of Activities [Section 2]).

Each patient's weight should be measured according to a standardized protocol and recorded on the eCRF to the nearest one-tenth kg. Waist circumference should be measured at midpoint, between lower margin of least palpable rib and top of iliac crest (approximately 1 inch (2.54 cm) above the navel), ([Appendix 7](#)).

Body mass index will be computed from the patient's weight and height. Body mass index should be rounded to the nearest whole number for purposes of Inclusion Criterion [4] (Section 6.1).

9.1.5. *Appropriateness of Assessments*

Efficacy and safety assessments included in this study are generally regarded as reliable and accurate with respect to the efficacy and safety assessments in individuals and populations with T2DM.

9.2. *Adverse Events*

Investigators are responsible for monitoring the safety of patients who have entered this study and for alerting Lilly or its designee to any event that seems unusual, even if this event may be considered an unanticipated benefit to the patient.

The investigator is responsible for the appropriate medical care of patients during the study.

Investigators must document their review of each laboratory safety report.

The investigator remains responsible for following, through an appropriate health care option: AEs that are serious or otherwise medically important, considered related to the investigational product or the study, or that caused the patient to discontinue the investigational product before completing the study. The patient should be followed until the event resolves and stabilizes with appropriate diagnostic evaluation. The frequency of follow-up evaluations of the AE is left to the discretion of the investigator.

Lack of drug effect is not an AE in clinical studies, because the purpose of the clinical study is to establish treatment effect.

After the ICF is signed, study site personnel will record via eCRF the occurrence and nature of each patient's preexisting conditions, including clinically significant signs and symptoms of the disease under treatment in the study. In addition, site personnel will record any change in the condition(s) and any new conditions as AEs. For each AE, the onset and duration, the seriousness and severity, and the actions taken with respect to study treatment will be recorded. Investigators should record their assessment of the potential relatedness of each AE to protocol procedure and investigational product via an eCRF.

Procedures and assessments performed prior to Visit 3 are considered screening procedures. The results of these procedures and assessments should be considered preexisting conditions and should be reported as medical history or concomitant illness.

The investigator will interpret and document whether or not an AE has a reasonable possibility of being related to study treatment, study device, or a study procedure, taking into account the disease, concomitant treatment, or pathologies.

A “reasonable possibility” means that there is a cause and effect relationship between the investigational product, study device and/or study procedure, and the AE.

The investigator answers yes/no when making this assessment.

Planned surgeries and nonsurgical interventions should not be reported as AEs unless the underlying medical condition has worsened during the course of the study.

If a patient’s investigational product is discontinued as a result of an AE, study site personnel must report this to Lilly or its designee via an eCRF, clarifying, if possible, the circumstances leading to any dosage modifications or discontinuations of treatment.

